8.2. Withdrawal from Study

If a subject prematurely withdraws from the study, the investigator will record the reason for withdrawal on the relevant eCRF. All subjects who withdraw from the study prematurely will be asked to have all ET assessments performed as soon as feasible and, unless consent has been withdrawn, will be asked to have a Safety Follow-Up phone call and visit approximately 1 week and 4 weeks after the last dose of study treatment, respectively. If a subject's last dose of study treatment was >1 week before the ET Visit, no additional phone call is needed; if a subject's last dose of study treatment was >4 weeks before the ET Visit, no additional visit is needed.

Reasons for withdrawal from the study include, but are not limited to:

- Withdrawal by the subject or parent(s)/legal guardian(s)
- AE
- Death

- Lost to follow-up
- Site terminated by Sponsor
- Study terminated by Sponsor
- Protocol deviation
- Investigator decision
- Sponsor decision

8.3. Sponsor's Termination or Suspension of Study or Study Site

The Sponsor or designee reserves the right to close a study site, terminate or suspend the entire study, or terminate or suspend the study at individual sites, at any time for any reason. If the study is prematurely terminated or suspended, the Sponsor shall promptly inform the investigators, the IRBs/IECs, the regulatory authorities, and any contract research organizations (CROs) used in the study of the reason for termination or suspension, as specified by the applicable regulatory requirements. The investigator shall promptly inform the subject and should assure appropriate therapy and/or follow-up.

9. STUDY ASSESSMENTS AND PROCEDURES

A schedule of assessments is provided in [Table 10](#) and [Table 11](#) (Appendix A). No study procedures should be performed until after signed informed consent is obtained from the parent(s)/legal guardian(s) and pediatric assent from the subject, if applicable (which may be done remotely, if allowed and remote consenting procedures are in place). Subject-related events and activities including specific instructions, procedures, concomitant medications, dispensing of study treatment, and descriptions of AEs should be recorded in the appropriate source documents and eCRFs.

9.1.

9.1.1.

[REDACTED]

[REDACTED]

9.1.2.

[REDACTED]

[REDACTED]

[REDACTED]

9.1.3.

[REDACTED]

9.1.4.

[REDACTED]

[REDACTED]

9.1.5.

[REDACTED]

[REDACTED]

9.1.6.

[REDACTED]

9.1.6.1.

[REDACTED]

9.1.6.2.

[REDACTED]

9.1.6.3.

[REDACTED]

[REDACTED]

9.1.6.4.

[REDACTED]

[REDACTED]

9.1.6.5.

[REDACTED]

[REDACTED]

9.1.7.

[REDACTED]

[REDACTED]

9.1.7.1.

[REDACTED]

[REDACTED]

[REDACTED]

[REDACTED]

[REDACTED]

[REDACTED]

[REDACTED]

[REDACTED]

[REDACTED]

[REDACTED]

[REDACTED]

[REDACTED]

[REDACTED]

[REDACTED]

[REDACTED]

9.1.7.2. [REDACTED]

[REDACTED]

[REDACTED]

9.1.7.3. [REDACTED]

[REDACTED]

- I [REDACTED]
- I [REDACTED]
- I [REDACTED]

9.1.8. [REDACTED]

[REDACTED]

9.2.

9.3. Safety Assessments

Concomitant medication use and AEs will be monitored throughout the study as described in [Section 7.1](#) and [Section 10](#), respectively. Additional safety assessments described in the following sections will be completed at the timepoints specified in the Schedule of Assessments ([Table 10](#) and Table 11).

For any abnormal safety assessment deemed clinically significant, the investigator will perform appropriate follow-up assessments (eg, repeat analysis), until the cause of the abnormality is determined and/or until the value returns to baseline (or within normal limits) or the investigator deems the abnormality to be of no clinical significance.

Clinically relevant findings occurring after informed consent and meeting the definition of an AE (new AE or worsening of a previously existing condition) must be recorded on an AE page of the eCRF.

Appropriate psychiatric evaluation and intervention will be provided for any treatment-emergent suicidal behavior or clinically significant suicidal ideation.

9.3.1. Medical History

For subjects who do not enroll directly from or participate in Study NBI-827104-CSWS2010, a medical history will be taken at the screening visit and updated on Day 1 and as needed throughout the study.

For subjects who enroll directly, a medical history will be taken to update the relevant history from Study NBI-827104-CSWS2010 on Day 1 and as needed throughout the study.

9.3.2. Body Weight

Body weight will be measured at the study visits indicated in the Schedules of Assessments (Table 10 and Table 11). The initial weight group assignment will be based on the subject's weight on Day 1.

9.3.3. Physical and Neurological Examination Including Height/Length and Tanner Staging

The complete physical examination will consist of an assessment of general appearance, extremities, skin and mucosae, head, eyes, ears, nose, throat, neck (including thyroid), lymph nodes, chest, lungs, cardiovascular, abdomen, genito-urinary, musculoskeletal, and neurological system, including assessment of level of consciousness, mental status, muscle strength and tone, coordination and gait, [REDACTED]

Height/length will be measured with subjects not wearing shoes. Height may be optional if the subject is unable to stand. If the investigator is unable to obtain height/length, the reason for noncollection must be captured in the eCRF. The physical examination schedule is provided in Table 10 and Table 11.

Physical signs of puberty will be assessed using Tanner staging as appropriate based on subject age and stage of puberty as part of the physical examination.

9.3.4. [REDACTED]

9.3.5. Vital Sign Measurements

Vital signs will be measured for the following: orthostatic systolic and diastolic blood pressure, orthostatic pulse rate, respiratory rate, and body temperature. Orthostatic blood pressures may be considered optional if the subject is unable to stand (eg, subject is in a wheelchair). If the investigator is unable to obtain orthostatic blood pressures, the reason for noncollection must be captured in the eCRF. Blood pressure and pulse rate will be measured using a calibrated

automatic blood pressure cuff after the subject has been supine for at least 5 minutes and after approximately 2 minutes standing, if possible.

Vital sign measurements will be obtained prior to study treatment administration on Day 1 or any scheduled blood sample collection, where applicable, at the timepoints specified in the Schedules of Assessments (Table 10 and Table 11).

9.3.6. Electrocardiogram

A standard 12-lead ECG will be recorded after the subject has rested supine for at least 5 minutes. The ECG should be performed in triplicate (at least 1 minute apart and within 15 minutes), if possible. The ECG will be centrally read and parameters that will be assessed include heart rate, PR interval, QRS duration, QT interval, and QTcF (machine readings or calculated). Additionally, the occurrence of de- and re-polarization and rhythm disorders or other abnormalities will be assessed. Based on the review of these parameters, the investigator will note if the ECG is Normal, Abnormal not Clinically Significant, or Abnormal Clinically Significant. If the ECG is Abnormal Clinically Significant, the investigator will provide a description of the abnormality recorded on the AE eCRF.

The ECG assessment should be performed prior to study treatment administration on Day 1, and prior to any blood sample collection at the timepoints specified in the Schedules of Assessments.

9.3.7. Clinical Laboratory Assessments

All clinical laboratory assessments will be performed by a central laboratory. The central laboratory will provide instructions and supplies to the study staff before study initiation and instructions will be included in a laboratory manual. The following clinical safety laboratory assays will be performed:

Hematology: complete blood count including white blood cell count with differential, red blood cell count, hemoglobin, hematocrit, and platelet count, mean corpuscular hemoglobin, mean corpuscular hemoglobin concentration, mean corpuscular volume, red cell distribution width, and mean platelet volume.

Clinical chemistry: sodium, potassium, calcium, magnesium, phosphorus, chloride, blood urea nitrogen, bicarbonate, creatinine, uric acid, albumin, alkaline phosphatase, lactate dehydrogenase, AST, ALT, GGT, creatine kinase, total bilirubin, total protein, glucose, [REDACTED].

Urinalysis: specific gravity, nitrite, ketones, protein, urobilinogen, glucose, bilirubin, leukocyte esterase, occult blood, and pH; microscopic examination of sediment will be performed only if the results of the urinalysis dipstick evaluation are positive for nitrite, protein, leukocyte esterase, or blood. Urine samples may be considered optional if the subject is unable to provide urine (eg, subject is in a diaper).

The following additional laboratory test will be performed at screening for subjects who do not enroll directly from or did not participate in Study NBI-827104-CSWS2010:

Serology: Blood will be collected for HIV-Ab, HBsAg, and HCV-Ab and reflex nucleic acid amplification testing (if applicable) at screening.

Drug screen: Urine will be collected at screening for cannabinoid drug testing.

[figure not shown]
Pregnancy test: Pregnancy tests will be performed throughout the study for female subjects of childbearing potential. A serum β -hCG pregnancy test will be performed at screening for subjects who do not enroll directly. A urine pregnancy test (using a urine pregnancy kit provided by the central laboratory) will be performed at the postscreening timepoints indicated in the Schedules of Assessments (Table 10 and Table 11). Female subjects who become of childbearing potential during the study will be required to undergo pregnancy testing at the timepoints indicated in the Schedule of Assessments (Table 10). Serum pregnancy tests should be performed if urine cannot be collected. Any positive urine pregnancy test should be confirmed by a serum pregnancy test.

9.3.8. Estimated Maximum Total Blood Sample Volume

The estimated maximum total blood volume for each subject collected during the study from screening (if applicable) to last visit (Safety Follow-Up Visit) is provided in Table 4.

Based on the blood volumes to be collected at the scheduled study visits, the blood volume collected will not exceed 3% of the total blood volume during a period of 4 weeks and will not exceed 1% at any single time.

Table 4:

9.3.9. Columbia-Suicide Severity Rating Scale

The C-SSRS is a validated instrument to prospectively assess suicidal ideation and behavior (<http://www.cssrs.columbia.edu>). There are versions of the questionnaire designed for use at screening (Children's Baseline version) and at baseline and visits throughout the study (Children's Since Last Contact version). All versions of the C-SSRS include a series of screening

questions related to suicidal ideation and suicidal behavior. Subject responses of “yes” to one or more screening questions will prompt additional questions that evaluate frequency and intensity of suicidal ideation and/or behavior.

The C-SSRS Children’s Version will be administered to subjects ≥ 6 years of age on Day 1. Younger subjects or subjects with developmental impairment for whom the C-SSRS would be inappropriate will be monitored for suicidality based on clinical impression. If the investigator is unable to conduct the C-SSRS screening, for example due to developmental disability, the reason for noncollection must be captured in the eCRF.

The C-SSRS will be administered and scored by the investigator or qualified personnel throughout the study as indicated in the Schedules of Assessments (Table 10 and Table 11).

9.4. Specific Study Period Information

A complete list of study assessments to be performed at the study center during the study periods by visit is provided in the Schedules of Assessments (Table 10 and Table 11).

Study visits during the Long-Term Treatment Period may be conducted remotely if individual in-person study visits at the study site are not possible due to Corona Virus Disease 2019 (COVID 19) related reasons (eg, subject is not able to travel to the site for safety reasons or as part of public health measures). In this situation, study treatment may be shipped directly to a subject. If any study visits during the Long-Term Treatment Period required to be conducted at the site are conducted via telephone or a tele-health platform, this will be documented in the source.

Assessments at these visits that must be conducted at the site (eg, [REDACTED]) may be rescheduled. Any visit assessments that are missed or conducted outside the visit window will be recorded as COVID-19 related protocol deviations.

9.4.1. Screening Period [REDACTED]

After providing parental or legal guardian informed consent with pediatric assent from developmentally capable subjects, subjects who do not enroll directly from or participate in Study NBI-827104-CSWS2010 will be screened to determine eligibility between [REDACTED] that may be completed in 1 or more visits.

At least 4 days of baseline [REDACTED] data should be collected during the Screening Period.

During screening, parent(s)/caregiver(s) of subjects who do not enroll directly from or participate in Study NBI-827104-CSWS2010 will be instructed or retrained by site personnel on how to self-administer the [REDACTED] at study visits.

All screening procedures must be completed, and results must be evaluated by the investigator before the procedures are performed on Day 1. Rescreening is permitted if a subject does not meet all eligibility requirements and returns to be rescreened. A subject that has failed screening twice may not be rescreened again without prior permission from the Sponsor.

Subjects who did not participate in Study NBI-827104-CSWS2010 and who do not meet inclusion criterion #2 and #3 (Section 5.2.1) at their initial screening in Study NBI-827104-CSWS2025 will not be eligible for rescreening.

9.4.1.1. Diagnosis Confirmation Panel

For subjects who did not participate in Study NBI-827104-CSWS2010, an external DCP will review and confirm that the subject meets the clinical diagnosis of EECSWS to determine study eligibility prior to Day 1. Medical history information, as well as any further medical information supporting the diagnosis if available (including the screening [REDACTED]), will be provided to the DCP to review to confirm the diagnosis. A DCP charter will describe the responsibilities and data review procedures.

9.4.2. Treatment Period [REDACTED]

9.4.2.1. Dose Titration Period [REDACTED]

Subjects who meet all of the inclusion criteria and none of the exclusion criteria are eligible to be enrolled into the study on Day 1.

For subjects who enroll directly from Study NBI-827104-CSWS2010, informed consent/assent will be provided on Day 1 or within 28 days prior to Day 1 before any assessments are performed for the current study. Medical history from Study NBI-827104-CSWS2010 will be updated. Parent(s)/caregiver(s) will be instructed on how to self-administer the [REDACTED] on Day 1 only if they were not trained during screening in Study NBI-827104-CSWS2010.

For subjects who do not enroll directly from or participate in Study NBI-827104-CSWS2010, medical history will be updated from screening on Day 1 and [REDACTED] may be performed up to 4 days prior to Day 1.

Vital signs, ECG, and clinical laboratory assessments should be performed before the first dose of study treatment is administered on Day 1. The first dose of study treatment will be taken at the study site.

Subjects will begin study treatment at DL 1 based on weight group on Day 1 ([Table 1](#)). Study treatment dose may be increased to DL 2 and DL 3 during the Dose Titration Period based on investigator judgment. [REDACTED] the study site will call the parent(s)/caregiver(s) to assess for any AEs and determine dose titration or adjustment.

9.4.2.2. Long-Term Treatment Periods A, B, and C [REDACTED]

Subjects may enter Long-Term Treatment Period B after completing the [REDACTED] Dose Titration Period. Subjects who do not tolerate DL 3 or who are otherwise not candidates for dose escalation will continue in Long-Term Treatment Period A at their highest tolerated DL (DL 1 to 3) until the [REDACTED] End of Long-Term Treatment Visit or ET. Dose escalation to DL 4 (and DL 5, if applicable) and treatment during Long-Term Treatment Periods B and C will be performed as described in [Section 4.1.3](#).

Tolerability of the subject's currently assigned DL will be assessed at each study visit. Investigator assessment of tolerability will include a review of AEs and [REDACTED] data as well as discussion with parent(s)/caregiver(s). Confirmation that these activities have been performed will be indicated in the eCRF.

Study Site Visits

Study assessments may be performed before or after the administration of study treatment, except on study visits in which dose is being changed () and . Subjects should withhold their study treatment on days of dose changes and until after completion of predose assessments. Additionally, vital sign measurements and ECG assessments should be performed prior to any blood sample collection.

Phone Calls

At certain timepoints in the study, phone calls with the study site will be used to perform assessments as indicated in the Schedule of Assessments (Table 10 and Table 11).

Discontinuation

Subjects receiving DL 3 or higher who discontinue study treatment at any time before the end of long-term treatment should undergo dose de-escalation if appropriate to avoid potential withdrawal seizures due to abrupt treatment discontinuation. The subject's current dose would be reduced, based on the investigator's judgment and medical urgency, in a stepwise manner over a period of up to . Guidance for implementing a more rapid de-escalation will be provided as needed to the investigator by the Medical Monitor on an individual basis based on clinical judgment. Subjects receiving DL 1 who discontinue study treatment do not require dose de-escalation. Subjects who discontinue study treatment will be withdrawn from the study.

9.4.3. Dose Taper Period

At the end of their final Long-Term Treatment Period (A, B, or C), subjects will begin the Dose Taper Period.

During the Dose Taper Period, the study treatment is tapered to avoid potential withdrawal seizures due to abrupt treatment discontinuation and ensure all subjects have discontinued NBI-827104 as shown in Table 5. Subjects who are receiving DL 1 or 2 at the end of their final Long-Term Treatment Period do not need to undergo dose tapering and can immediately enter the Safety Follow-Up Period.

Table 5: Dose Taper Procedure

Dose Level at End of Long-Term Treatment Period	Dose Level During Taper Period		
Dose Level 1 or 2	Off treatment (start Safety Follow-Up)	Not applicable (Safety Follow-Up)	
Dose Level 3	Dose Level 2	Off treatment (start Safety Follow-Up)	Not applicable (Safety Follow-Up)
Dose Level 4	Dose Level 3	Dose Level 2	Off treatment (start Safety Follow-Up)
Dose Level 5	Dose Level 4	Dose Level 3	Dose Level 2

9.4.4. Safety Follow-Up Period [REDACTED]

9.4.4.1. Safety Follow-Up Call [REDACTED]

During the Safety Follow-Up Period, approximately [REDACTED] after the last dose of study treatment, the study site will call the parent(s)/caregiver(s) to collect AE information.

9.4.4.2. End of Study [REDACTED]

The Safety Follow-Up Visit is the final study visit.

10. ADVERSE EVENTS

All AEs, whether observed by the investigator, reported by the subject, noted from laboratory findings, or identified by other means, will be recorded from the time the subject has signed the informed consent form (ICF) (for subjects who do not enroll directly from or participate in Study NBI-827104-CSWS2010) or Day 1 (for subjects who enroll directly) until the subject's final study visit (or upon ET).

10.1. Definition

An AE is any untoward medical occurrence in a patient or clinical investigation subject administered a pharmaceutical product that occurs after enrollment into the study and which does not necessarily have a causal relationship with the study treatment. An AE can therefore be any unfavorable and unintended sign (including an abnormal laboratory finding, for example), symptom, or disease temporally associated with the use of a medicinal product, whether or not considered related to the medicinal product.

A treatment-emergent adverse event (TEAE) is an AE that started or worsened in severity following the first dose of study treatment.

Adverse events include, but are not limited to, any of the following:

- Worsening or change in nature, severity, or frequency of conditions present at the start of the study
- Subject deterioration beyond what would be expected due to the primary illness
- Intercurrent illness
- Drug interaction

All suicidal behaviors and clinically significant suicidal ideations will be documented as an AE.

Subjects or parent(s)/caregiver(s) should be questioned in a general way, without asking about the occurrence of any specific symptom. The investigator should attempt to establish a diagnosis of the event based on signs, symptoms, and/or other clinical information. In such cases, the diagnosis should be documented as the AE and not the individual signs/symptoms. Following questioning and evaluation, all AEs, whether believed by the investigator to be related or unrelated to the study treatment, must be documented in the subject's medical records, in accordance with the investigator's normal clinical practice and on the AE eCRF. Each AE is to be evaluated for duration, intensity, frequency, seriousness, outcome, other actions taken, and relationship to the study treatment.

The following are not considered AEs:

- Seizures will not be considered an AE unless there is a significant increase in seizure frequency, a new seizure type, occurrence of status epilepticus, and/or in the investigator's opinion it should be captured as an AE.
- Continuous persistent disease/symptom present before study treatment administration, unless it unexpectedly progresses, or increases in severity following study treatment administration

- Study treatment failure or lack of efficacy
- Pregnancy
- Overdose of either study treatment or concomitant medication without any clinical signs or symptoms

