10.4.1. Definition of a Serious Adverse Event

An SAE is any AE that results in any of the following outcome:

- Death.
- A life-threatening AE. Life-threatening means that the subject was, in the view of the investigator or Sponsor, at immediate risk of death from the reaction as it occurred. It does not mean that hypothetically the event might have caused death if it occurred in a more serious form.
- Inpatient hospitalization or prolongation of existing hospitalization. Hospitalization for elective treatment or a preexisting condition that did not worsen during the clinical investigation is not considered an AE. Hospitalization or nursing home admission for the purpose of caregiver respite is not considered an AE. Complications that occur during hospitalization are AEs, and if a complication prolongs hospitalization, the event is considered serious. Treatment in a hospital emergency room is not a hospitalization.
- A persistent or significant incapacity or substantial disruption of a person's ability to conduct normal life functions.
- A congenital anomaly/birth defect.
- Important medical events that may not result in death, be life-threatening, or require hospitalization. These events may be considered serious when, based on appropriate medical judgment, they may jeopardize the health of the subject and may require medical or surgical intervention to prevent one of the outcomes listed. Any other event thought by the investigator to be serious should also be reported, following the reporting requirements detailed in this section. Examples of such medical events include allergic bronchospasm requiring intensive treatment in an emergency room or at home, blood dyscrasias, convulsions that do not result in inpatient hospitalization, or the development of drug dependency or drug abuse.

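### The seizure exception in the AE definition has no seriousness trigger, so whether a serious habitual-type seizure counts in the primary endpoint is left to the investigator

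*Protocol*

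**What the plan says.** Protocol Section 10.1 lists seizures among the things that are not AEs, with exceptions: "Seizures will not be considered an AE unless there is a significant increase in seizure frequency, a new seizure type, occurrence of status epilepticus". The sentence ends with a fourth, open condition, the investigator's "opinion it should be captured as an AE". Section 8.1 sends the reader to Section 10.1 to decide whether a seizure is an AE.

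Section 10.4.1 makes every SAE an AE first: "An SAE is any AE that results in any of the following outcome". Three later statements there bear on seizures:

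- Its examples of important medical events include "convulsions that do not result in inpatient hospitalization". The governing sentence is conditional: "These events may be considered serious when, based on appropriate medical judgment, they may jeopardize the health of the subject".
- Under inpatient hospitalization: "Hospitalization for elective treatment or a preexisting condition that did not worsen during the clinical investigation is not considered an AE".
- A general instruction: "Any other event thought by the investigator to be serious should also be reported".

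None of the three refers to the seizure exception. Section 11.4.1 makes the occurrence of serious TEAEs the primary endpoint. SAP Section 9.2 tabulates treatment-emergent SAEs by SOC and PT, adds an SAE listing, and gives no separate rule for seizures.

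**The concern.** Every child in this study has an epileptic encephalopathy, so seizures are a foreseeable route to hospital. The protocol itself treats them as a safety matter: Section 4.1.2 mentions breakthrough seizures when discussing titration, and the taper exists to avoid withdrawal seizures. Yet the rule that removes seizures from the AE definition gives them no way back on grounds of seriousness other than the investigator's choice.

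Three things are at stake:

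- **The primary endpoint.** Two centers could see the same admission and record it differently, each within the protocol.
- **SAE reporting.** The 24-hour duty in Section 10.4.3 applies to SAEs. An admission not recorded as an AE does not clearly fall under it.
- **Safety review.** The sponsor and the DMC review safety data when deciding whether the study continues and whether DL 5 is opened (Section 11.6.2). Uneven capture would carry into that review. With a single open-label arm, no comparator shares the same misclassification.

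**Working it through.** The documents give no figure to reproduce here: no expected event rate, no hypothesis test (Section 11.1), and a sample size carried over from the parent study (Section 11.2). The check is a walk through the text, followed by arithmetic for scale.

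**Test case.** A child has a seizure of the usual type. Frequency is unchanged and there is no status epilepticus. The child is admitted to hospital.

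1. *Section 10.1, three event-based conditions.* Frequency increase: no. New type: no. Status epilepticus: no.
2. *Section 10.1, fourth condition.* The investigator may capture the seizure but need not. The admission is not named as a reason to do so.
3. *Section 10.4.1, opening.* If step 2 ends in no, the event is not an AE. It therefore cannot be an SAE, nor a serious TEAE under Section 11.4.1.
4. *Section 10.4.1, text favoring capture.* Non-hospitalized convulsions are an example of an important medical event, and events the investigator thinks serious should also be reported. Both rest on judgment.
5. *Section 10.4.1, text against capture.* Admission for a preexisting condition that did not worsen is not an AE. A site can read a habitual seizure that way.
6. *SAP Section 9.2.* It works from recorded AEs, so it cannot recover an event lost at step 2.

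Replacing admission with a life-threatening or fatal seizure of the usual type leaves steps 1 to 3 unchanged. Admission is where I would expect practice to vary most.

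**Scale.** Inputs: N = 24 (Section 11.2, up to approximately 24 subjects) and about 24 centers (Synopsis). The average is 24/24 = 1 subject per center, so differences between centers in reading the rule become differences between subjects.

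If k subjects have a seizure as their only serious event, and its classification depends on the site, the incidence shifts by k/N. The counts k are assumptions:

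- k = 1: 1/24 = 4.2 percentage points
- k = 2: 2/24 = 8.3 points
- k = 3: 3/24 = 12.5 points

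For comparison, exact (Clopper-Pearson) 95% intervals at N = 24 are 0 to 14.2% for 0 events, 0.1 to 21.1% for 1, 1.0 to 27.0% for 2, and 2.7 to 32.4% for 3. A shift of one or two subjects lies within the sampling uncertainty, but it is avoidable and those intervals do not reflect it.

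**The case against.** The strongest reply is that the sections do not conflict. Section 10.4.1 is nested in Section 10.1, and Section 8.1 confirms that Section 10.1 governs, so a site is not choosing between two rules. The investigator-opinion condition admits any serious seizure. The general AE bullets in Section 10.1 also cover worsening in nature, severity or frequency of an existing condition, and deterioration beyond what the illness would explain. The sentence on unworsened preexisting conditions suggests that leaving habitual seizures out was deliberate. Recorded seizure SAEs are already separable by preferred term.

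Much of this stands. A reader might infer that Sections 10.1 and 10.4.1 classify the same seizure in opposite ways, or that following Section 10.4.1 would inflate the count. The text does not support either: the convulsion example applies only to events that are already AEs, and then only on medical judgment. A reader might also infer that serious seizures are shut out. They are not; their capture is simply not required.

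What the reply does not remove is the discretion. The seizure-specific sentence names frequency and type but neither severity nor seriousness, while the general bullets include severity. If the omission was deliberate, the protocol should say so for seizures, because the primary endpoint depends on it. Section 9.1 and the non-primary endpoints are redacted and may provide for seizure capture elsewhere, but the visible text sets AE and SAE status.

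**Conclusion.** The concern holds in a limited form. Whether a habitual-type seizure that is fatal, is life-threatening or leads to hospitalization counts in the primary endpoint and is reported as an SAE depends on investigator discretion, and Section 10.4.1 gives unlinked signals in both directions. This should be corrected because it concerns primary-endpoint capture and safety reporting.

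The size is 4.2 percentage points of incidence per subject affected, assuming N = 24 and that the seizure is that subject's only serious event. It is tempting to quote a total shift by supposing a number of affected subjects, but the documents give no rate from which to choose one. The consequence is limited to the consistency of a descriptive incidence: there is no test, and hence no alpha or power, to disturb.

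**What to change.** 1. In Section 10.1, add to the seizure exceptions: *or the seizure results in death, is life-threatening, or results in inpatient hospitalization or its prolongation*. Naming these outcomes, instead of pointing to the whole SAE definition, avoids circularity with the convulsion example.
2. In Section 10.4.1, cross-reference Section 10.1 from both the convulsion example and the sentence on hospitalization for a preexisting condition. The second reference is essential: if that sentence stays as it is, the new trigger would contradict it.
3. Optionally, show serious TEAEs in the SAP with and without seizure terms. This adds little, because SAP Section 9.2 already gives treatment-emergent SAEs by SOC and PT and lists SAEs. It cannot recover events that were never recorded.

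The cost is a short protocol clarification, a memo to sites and a few more SAE reports. Nothing in treatment or visits changes.
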